8.7.3 Feature Analysis

Additional analyses will be performed using the specific features from the Pivotal Study to discriminate benign from cancer using classification methodology. Six specific pre-defined OA features will be scored by the independent readers using a 0-5 or 0-6 ordinal scale to evaluate: 1) internal vascularity and deoxygenation, 2) internal deoxygenated blush, 3) internal total blood 4) peri-tumoral boundary zone vascularity and deoxygenation,), 5) external peri-tumoral radiating vessels, and 6) interfering artifact. The first three features are considered to be internal features and will also be summed to derive a total internal feature score. Similarly, the fourth and fifth feature will be summed to derive a total external feature score. Also the five feature scores will also be summed to derive a total score. The distributions

Seno Clinical Study Protocol: PIONEER-01
300176 Rev 8 PIONEER 01 Protocol Amendment 3.2

of the benign vs. malignant masses will be performed using a Wilcoxon Rank Sum test for individual features and ANOVA for the three total scores.

8.7.4 Other Secondary Analyses

The sensitivity, specificity, concordance, PPV, NPV, PLR, NLR, and odds ratio for Imagio and the Imagio ultrasound component will be displayed for 2% POM and assessed using 99% confidence bounds.

Additionally, sensitivity and specificity results will be separately displayed for Imagio and the Imagio ultrasound component for the pre-defined subpopulations as descriptive statistics.

8.7.5 BI-RADS Analyses

Results will be displayed according to the BI-RADS classification to provide insight into currently used guidelines. The matched pairs cross tabulation of Imagio versus its' ultrasound component will be assessed.

The ability of Imagio to downgrade BI-RADS 4a and 4b (or BI-RADS 3) relative to IUS and separately according to the site investigator to BI-RADS 3 (or BI-RADS 1-2) for the benign cases and to then symmetrically upgrade BI-RADS 3, 4a, 4b, and 4c according to Imagio relative to IUS and separately relative to the site investigator for the cancer cases; the discordant pairs will be compared using a McNemar's test for individual readers and a generalized linear model for grouping readers. In addition, the ability of Imagio to improve the site investigator classification for the BI-RADS 4ab (or BI-RADS 3) subgroup will be assessed separately for the cancer and benign cases; the percents (Imagio positive vs. Imagio negative) will be separately evaluated using a two-sided Fisher Exact Test.

8.7.6 Histopathology Analyses

Results for cancers, benign cases, and high risk cases will be separately displayed to see if Imagio features are correlated with histopathology outcomes.

8.7.7 Other Analyses

The sensitivity and specificity for Imagio and the Imagio ultrasound component will be generated for individual readers. The learning curve of individual readers will also be assessed in units of at least 100 cancers and at least 200 benigns to check if sensitivities and specificities improve as more cases are read.

Inter-reader variation will be evaluated separately for cancer cases and for benign cases for the readers. Inter-reader variability for these two subsets (cancers, benigns) will be analyzed using an ANOVA model where the readers are considered to be fixed effects; a random effects model will also be run. Intra-reader variation will be evaluated using paired t-tests applied to the paired POMs, and BI-RADS separately for cancer cases and for benign cases.

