All subjects not undergoing an immediate biopsy will be followed for an additional 12 months with an Imagio evaluation at the end of the 12 month follow-up. If possible, for subject management efficiency, once the subject agrees to participate in the study and her biopsy date is determined, then she can be scheduled for Imagio evaluation after the biopsy decision and scheduling, but prior to the biopsy. Follow-up will end when the subject undergoes a biopsy prior to 12 months or once the subject has been followed for 12 months. The decision to biopsy will be made solely by the site according to best practice without considering the Imagio evaluation outcome, but may include the CDU evaluation; if a biopsy is to be performed, then the biopsy specimen may be evaluated by an independent histopathologist.

[figure not shown]

Figure 3: Subject Screening, Enrollment, Evaluation, and Possible Follow-up

¹The decision to biopsy is made upon investigational site's standard of care and not based on the Imagio evaluation

A multi-reader, multi-case (MRMC) methodology will be used for the Pivotal Study where 7 independent radiologists passing prospective proficiency criteria will evaluate each of the Pivotal Study subjects for the registration reads (Imagio and IUS image sets) and 3 other qualified independent radiologists will share the evaluation of each of the Pivotal Study subjects for the reimbursement reads. The total number of subjects depends on accruing at least 1,000 benign masses and if there is not a sufficient number then the total number of masses may increase slightly to achieve the minimum number of 1,000 benign masses. The readers will also reread 5% of the registration cases and 2.5% of the reimbursement cases to assess temporal trends intra-observer variability and consistency.

Each registration reader will review the data from two image sets (IUS and Imagio) for each case; each independent reader will evaluate Imagio according to a pre-determined diagnostic rule set based on OA image characteristics and will similarly evaluate IUS according to another pre-determined diagnostic rule set where each reader will estimate the probability that the mass is cancer on a scale from 0% to 100% in 5% increments (1% if \leq 10% or \geq 90%). Readers will assess the image sets in the following pre-defined order during independent review sessions; this pre-defined order is consistent with medical practice: Imagio diagnostic ultrasound alone (IUS)

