All registration readers will be tested and selected prior to making any further Pivotal Study reads for subjects 101 and beyond which will constitute the Pivotal Study. All effectiveness analyses will be conducted at the mass-level; it is projected that no more than 5% of all subjects will have multiple masses. A minimum of 100 Pilot Study cases and 1,700 Pivotal Study cases must pass QA review and must not be enrollment failures to be included in the respective Pilot and Pivotal Study analyses. Enrollment will continue until there are 100 Pilot Study cases and at least 1,700 Pivotal Study cases that pass both criteria. The 100 Pilot Study cases will be used for education, training, and publication purposes; only the Pivotal Study cases will be used to support Imagio registration for this indication for use.

All selected registration readers will evaluate all masses that pass QA review according to a MRMC design for the pivotal phase. To mimic the real world setting as closely as possible, all readers will receive respective feedback on the histopathology results after completing their locked evaluations; readers may not change results after receiving feedback.

For the Pivotal Study component, subsets of 5% of registration image sets and 2.5% of all reimbursement image sets will be reread to assess learning and consistency; the first reads will be used in the data analyses for registration and reimbursement. Readers will be required to turn in their evaluations before conducting the rereads which will be conducted once the respective reader completes their Pivotal Study reads.

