The final sample size of the Pivotal Study will be determined by an interim analysis after the first 800 Pivotal Study subjects (cases 101-900 passing Quality Assurance review) have been evaluated with Imagio plus the results of any pre-scheduled biopsies; the final sample size will depend on the numbers of masses biopsied, the percent of biopsied masses with a cancer diagnosis, and the sensitivities and specificities for Imagio and IUS among biopsied masses. The interim analysis will be conducted once at least four of the seven registration readers complete the review of the 800 cases. Results will be shared with partners for business planning purposes based on all 7 registration readers but will not be shared with sites or published until the study is completed. The final sample size will not exceed 2,400 masses.

The study design will require all images to be managed by an independent ICC according to FDA guidelines (FDA Clinical Performance Evaluation: Considerations for Computer-Assisted Detection Devices Applied to Radiology Images and Radiology Device Data – Pre-market Approval [PMA] and Pre-market Notification [510k] Submissions, October 21, 2009). The ICC will assign multiple readers per team to review all images leading to the decision to either perform a biopsy or to follow the subject for up to 12 months. To best replicate clinical relevance where mammography and conventional diagnostic ultrasound will be read first in practice, the image sets will be read in the following order:

- 1. Imagio diagnostic ultrasound alone
- 2. Imagio (diagnostic ultrasound plus opto-acoustics).

To preserve their independence and objectivity as well as to minimize bias, the independent readers must lock their IUS evaluations before being allowed to begin their Imagio evaluations; in addition, readers will NOT have access to any clinical data but will have access to biopsy outcomes once they record and lock their evaluations. Then readers will have controlled access to biopsy outcomes in units of 25 cases to simulate the real world setting where practicing radiologists receive outcomes.

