9.8. Imaging Coordination Committee (ICC)

An independent ICC will coordinate the reviews of all possible image sets consisting of data used to make the diagnosis leading to biopsy as well as Imagio. The ICC will oversee three QA reviewers to ensure that the image sets were collected by sites as instructed and to make sure that cases are properly blinded. A separate ICC protocol will describe and govern the image review process. There will be 7 independent registration readers and 3 independent reimbursement readers for the Pivotal Study to perform these reviews. Readers will be directed to read the image sets in a predefined order to correspond to real world setting and to also receive real time feedback every 25 completed cases to further correspond to real world setting.

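### The only planned intra-reader analysis, a paired t-test, can show drift or learning but cannot measure the repeatability that the rereads are also meant to assess

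*Protocol*

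**What the plan says.** Section 8.7.7 fixes the method: "Intra-reader variation will be evaluated using paired t-tests applied to the paired POMs, and BI-RADS separately for cancer cases and for benign cases". The protocol names no other intra-reader statistic: no ICC, kappa, limits of agreement, within-reader SD, or rate of change at the 2% POM threshold.

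The rereads have more than one purpose. Section 3.1: "The readers will also reread 5% of the registration cases and 2.5% of the reimbursement cases to assess temporal trends intra-observer variability and consistency". Section 3.2: "subsets of 5% of registration image sets and 2.5% of all reimbursement image sets will be reread to assess learning and consistency".

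The order of events matters as well. Section 3.2 states that "all readers will receive respective feedback on the histopathology results after completing their locked evaluations", and Section 8.1.1 adds that "readers will have controlled access to biopsy outcomes in units of 25 cases". The rereads come last; Section 3.2 describes "rereads which will be conducted once the respective reader completes their Pivotal Study reads".

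**The concern.** Variation within a reader is the spread of the differences between first and second reads. A paired t-test uses that spread as its error term and tests the mean. More scatter makes a significant result less likely, and a reader whose second scores are unrelated to the first, with no net shift, will usually give a non-significant result. If that result is then presented as evidence of consistency, it rests on nothing. BI-RADS is also an ordered category with subclasses 4a to 4c, so a t-test on it needs arbitrary numeric scores.

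The second issue is separate. For biopsied cases, the reader has been given the histology before rereading the same images, so the second read may not be independent of the truth.

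At stake is whether the reread exercise, done by all seven registration readers, can support any statement about their repeatability.

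**Working it through.** The protocol gives no sample size, power or acceptance limit for this analysis, so there is no planned figure to reproduce.

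**1. Number of pairs.** Inputs: 5% reread (Sections 3.1, 3.2); at least 1,700 Pivotal cases (Section 3.2); cap of 2,400 masses (Section 8.6.1); at least 1,000 benign masses (Section 3.1).
- 0.05 × 1,700 = 85 per reader; 0.05 × 2,400 = 120.
- Assume 1,000 of the 1,700 are benign and the rest cancer: 0.05 × 1,000 = 50 benign pairs and 0.05 × 700 = 35 cancer pairs. High-risk lesions would reduce these numbers. The planned tests are the two split ones, not a pooled test of 85.

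**2. What the test responds to.** With d = second read − first read, t = mean(d) / (SD(d)/√n). If the true mean of d is zero, the rejection rate is the chosen level, whatever SD(d) is. The protocol sets no level for this test; 5% is assumed here. A simulation at n = 85 (20,000 runs) gave 4.7% to 5.1% for SD(d) of 2, 10, 20 and 30 POM points. The corresponding limits of agreement, 1.96 × SD, run from about ±4 to ±59 points. These SDs are assumptions.

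**3. The same on the protocol's POM scale.** Paired reads with no mean shift were simulated on the protocol's grid (3,000 runs per cell, simulation error about 0.4 percentage points). The POM distribution is assumed: latent normal, mean −1.5, SD 1.2 on the probit scale. Results for 50 pairs:

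| Latent read–reread correlation | Mean ICC | Pairs changing side of 2% POM | t-test rejects at 5% |
|---|---|---|---|
| 0.95 | 0.93 | 9% | 6.1% |
| 0.8 | 0.74 | 19% | 4.6% |
| 0.5 | 0.42 | 31% | 4.5% |
| 0.2 | 0.15 | 40% | 4.8% |
| 0 | 0.00 | 46% | 4.4% |

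The ICC and the threshold-crossing rate separate the rows; the t-test does not. At 35 pairs the rejection rates are 4.4% to 5.5%.

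**4. Extreme case.** Let 25 masses go from 1% to 40% and 25 from 40% to 1%. The mean difference is 0, t = 0 and p = 1.00, yet every mass changes side of the 2% threshold.

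**5. The converse.** Assume a uniform 1-point shift with read error SD 1 and case SD 20, so that the ICC is 0.996. The t-test rejects in 98% of runs at 35 pairs and 99.9% at 50. A nearly perfect reader is flagged.

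**6. A real shift.** For an assumed 3-point drift, the signal is 3√n/SD.
- At n = 85: 3 × 9.22/10 = 2.77 (simulated power 78%) and 3 × 9.22/30 = 0.92 (15%).
- In the split tests at SD 10: 3 × 7.07/10 = 2.12 for 50 pairs and 3 × 5.92/10 = 1.77 for 35.

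Even as a drift check, the test is weaker than the pooled figure suggests, and weaker still for an erratic reader.

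**7. Feedback before rereads.** Outcomes are released every 25 cases after locking (Sections 8.1.1, 9.8), and rereads follow all Pivotal reads (Section 3.2). The protocol does not hold back feedback for the reread subset. To see the direction of the effect, 50 benign pairs were simulated at latent correlation 0.5, with a recalled share q scored 1% on reread:

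| q | t-test rejects at 5% | Mean ICC |
|---|---|---|
| 0 | 5% | 0.42 |
| 0.2 | 16% | 0.36 |
| 0.5 | 63% | 0.24 |

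In this model recall creates a mean shift and lowers measured agreement. It does not hide poor repeatability.

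**The case against.** The strongest reply is that the rereads are also meant to show learning and temporal trends, for which comparing mean first and second reads is sensible. That stands, and it is why the t-test should stay and not be replaced.

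A reader might infer that an inconsistent reader would pass. The protocol states no acceptance rule and does not say that a non-significant result will be taken as proof of consistency. What stands is narrower: the planned statistic cannot support a statement about consistency.

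A reader might also infer that histology feedback makes poor repeatability invisible. The documents do not support that. Histology exists only for biopsied masses, actual recall after at least 1,700 cases is unknown, and the illustration above shows contamination, not concealment. Feedback is also a deliberate design choice meant to resemble practice. Sections 5.8 and 5.13 deny readers access to biopsy outcomes or the histopathology report; Section 8.1.1 allows access once evaluations are locked, so the feedback provisions remain in force.

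Finally, this is a supplementary analysis, and an analysis plan could add agreement measures without contradicting Section 8.7.7. That limits the weight of the point. It does not remove it, because the protocol fixes a specific method that misses one of its own stated purposes. For BI-RADS, no calculation was run to show that a t-test misleads about a mean shift; the objection there rests on the scale alone.

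**Conclusion.** The point holds as a limited one. Following Section 8.7.7 as written, the trial can report drift between first and second reads but not intra-observer variability or consistency. The 5% rejection rate under no mean shift is a property of the test and does not depend on the assumed POM distribution. The ICC values, threshold-crossing rates, power figures and recall results do depend on assumptions and are illustrative. The benign and cancer pair counts assume the minimum benign number at 1,700 cases.

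Prior feedback is a real but separate qualification for biopsied reread cases, of unknown size. It would be wrong to infer that the registration results are undermined: Sections 3.2 and 8.1.1 use first reads for analysis, and the reread comparison feeds none of the six hypotheses or the sample size. The change is worth making because it is cheap and the data are already planned.

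**What to change.** In Section 8.7.7:
- Keep the paired comparison, label it a check for drift or learning, and state that non-significance is not evidence of consistency.
- Add, by truth status and with confidence intervals: within-reader SD or limits of agreement and ICC for POM; weighted kappa for BI-RADS; and percent agreement on the 2% POM call.
- State that reread agreement for biopsied cases may be influenced by earlier histology feedback.
- Where feasible, select the reread cases in advance and defer their feedback in a way that does not reveal to readers which cases they are, for example by not leaving visible gaps in each block of 25.

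The added statistics cost only analysis wording and programming; no new reads are needed. Deferring feedback on about 85 cases per reader has an operational cost, and if done visibly it could flag those cases, so it is optional. If it is not done, the reporting caveat is enough.

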8.8. Other Assessments or Analyses

Specific treatment-emergent adverse events will also be displayed for each subject.

9. ADMINISTRATIVE CONSIDERATIONS

9.1. Investigators and Study Administrative Structure

Each site will have a designated investigator and one or more study coordinators collectively responsible for the conduct of the study inclusive of referral, screening, enrollment, evaluation, documentation, and subsequent biopsy in accordance with Good Clinical Practice (GCP) compliance.

9.2. Institutional Review Board (IRB)

The protocol and the informed consent form, and any other institution-specific documents, must have the approval of a properly constituted IRB committee responsible for approving clinical studies. The signed IRB approval letter must specify the date of protocol and informed consent form approval and identify the documents approved including the investigator's name, the protocol version, date and title. Any subject materials or advertisements used to recruit subjects should also be reviewed and approved by the IRB. Clinical supplies will not be shipped until a signed approval letter from the IRB has been received and a contractual agreement has been signed by the sponsor or sponsor's authorized representative and the clinical site.

9.3. Ethical Conduct of the Study

This study will be conducted in accordance with Title 21 Code of Federal Regulations (CFR) Parts 50, 54, 56 812, and 820.30 as well as the ethical principles outlined in the ICH GCP guidelines, the standard ISO 14155; ICH E6, E9, E14, E15 and in accordance with all local requirements.

9.4. Informed Consent

A written Informed Consent Form (ICF) must be obtained from the subject prior to performing any study-related procedures. The investigator or investigator's designee will provide background information on the study, including the benefits and risks of all study-related procedures. The investigator or investigator's designee will also encourage the prospective subject to ask questions about the study and will provide the subject with sufficient opportunity to consider whether or not to participate. After written consent/assent has been documented, previously obtained clinical radiographic data can be used for the study.

Original signed informed consent forms must be filed in the subject records at the site. A copy of the signed consent/assent form should also be provided to the subject.

Seno Clinical Study Protocol: PIONEER-01 300176 Rev 8 PIONEER 01 Protocol Amendment 3.2

The ICF template for this study may be revised by an investigator or an IRB based on the institution's requirements for a non-significant risk device. However, all changes requested by an investigator or an IRB, even those that may not be considered substantial and/or do not affect the rights, safety or welfare of a subject, must be approved by the sponsor. If the sponsor determines that the revisions are substantial and/or affect the rights, safety or welfare of a subject, the ICF must be reviewed and approved by both the sponsor and IRB before the ICF can be utilized. Copies of the current ICF's are attached in Appendix B.

9.5. Subject Confidentiality

Confidentiality will be maintained in accordance with HIPAA as per Title 45 CFR Part 164.508. Subject names must not be revealed to the sponsor or sponsor's authorized representatives. Only the subject identifier (number and initials) will be recorded in the eCRF and if the subject's name appears on any other document, it must be redacted and replaced with the subject identifier before a copy of the document is supplied to the sponsor or sponsor's authorized representatives. Study findings stored on a computer will be stored in accordance with local data protection laws. In the event of inadvertent communication of such information, immediate steps to redact the information from all study files will be implemented, with appropriate documentation in the subject study file.

9.6. Study Monitoring

Seno or their designate will schedule and conduct regular on-site visits for monitoring of study activities and data recording in order to verify data accuracy as well as protocol and regulatory compliance. Review of the eCRFs at the investigational site will be conducted to confirm completeness and clarity, to verify eCRF data against source documents and to clarify administrative matters. Formal reports of these visits will be generated with copies provided to the Seno Director of Clinical Operations or designee for review and approval and/or designated sponsor representatives.

9.7. Case Report Forms and Study Records

Data will be recorded using an electronic data capture (EDC) system. An EDC Database Programmer will develop and test the database in a validated environment according to the requirements of 21 CFR Part 11, Electronic Records; Electronic Signatures. Highlights of the software development lifecycle process include database development according to a validation protocol that documents the design requirements and specifications, database testing by EDC programmers and the CRO Data Management end users using test eCRFs, and documented review by the CRO and acceptance by Seno. The database is considered validated when the expected results are the same as the actual results, and the end users verify that the database performs according to the requirements.

The validation report, design procedures, testing results, source code, and test eCRF cases are filed in the central files. Database maintenance will be provided throughout the study, as well as user support and administration (access and site user rights set-up, removal, etc.)

Seno Clinical Study Protocol: PIONEER-01 300176 Rev 8 PIONEER 01 Protocol Amendment 3.2

The MedDRA dictionary will be used to code adverse events.

The investigator is responsible for maintaining adequate and accurate medical records from which information will be transferred into the study database. Study-specific eCRFs should be completed by the investigator or designated personnel. Detailed instructions will be provided with the implementation of access to the eCRF.

